#### Part 2 (Phase III)

Except for potential criteria, which will be confirmed after analysis of Phase IIb results, the same criteria as Part 1 (Phase IIb) will need to be met.

## 3.3.4 Discontinuation of trial participants from treatment or assessments

Trial participants may discontinue trial treatment or withdraw consent to trial participation as a whole ("withdrawal of consent") with very different implications; please see Section 3.3.4.1 and Section 3.3.4.2.

In case of premature permanent discontinuation of trial treatment, the	EOT visit procedures
will be done at the earliest, followed by a safety follow up visit	after the last drug
administration. For those trial participants with premature discontinua	ition happening before
visit 14 in addition to safety follow up assessment, trial pa	rticipants ideally should
also continue visits for assessment of efficacy up to Visit 14	as per Flowchart. For
these cases only the IMP administration will be skip.	_

The decision to discontinue trial treatment or withdraw consent to trial participation and the reason must be documented in the source documents and in the CRF.

Measures to control the withdrawal rate include careful trial participant selection, appropriate explanation of the trial requirements and procedures prior to trial enrolment, as well as the explanation of the consequences of withdrawal.

Page 56 of 177

Proprietary confidential information © 2023 Boehringer Ingelheim International GmbH or one or more of its affiliated companies

If the reason for discontinuation is an AE, please follow the requirements for AE collection reporting (see Section 5.2.6.2). If the reason for discontinuation is death, this should be reported on the SAE form as well, regardless of causal relationship.

#### 3.3.4.1 Discontinuation of trial treatment

An individual trial participant will discontinue trial treatment if:

- The trial participant wants to discontinue trial treatment. The trial participant will be asked to explain the reasons but has the right to refuse to answer.
- The trial participant has repeatedly shown to be non-compliant with important trial procedures and, in the opinion of the investigator, the safety of the trial participant cannot be guaranteed as participant is not willing or able to adhere to the trial requirements in the future.
- The trial participant uses/requires certain restricted medications, such as immunosuppressive / immunomodulatory biologics, investigational products/devices, IL-36 receptor inhibitors (as mentioned in Section 4.2.2), for any indication.
- The trial participant can no longer receive trial treatment as per physician's discretion (such as surgery, adverse events, other diseases)
- The trial participant should not receive subsequent doses of trial treatment if a hepatic injury alert (see Section 5.2.6.1.4) is confirmed without identification of an alternative cause in the work-up according to the "DILI checklist".
- The trial participant develops suicidal ideation of type 4 or 5 in the Columbia-Suicide Severity rating Scale (C-SSRS) or any suicidal behaviour (see Section 4.2.1 on Individual stopping rules related to specific AEs)
- The trial participant is unable to receive trial treatment consecutively for more for any reason
- If the participant experiences an infection with SARS CoV 2 (as confirmed by local standards) or any significant systemic infection based on the investigator's judgement, interruption of study medication should be considered. The participant may resume trial treatment following recovery of the infection if the participant is expected to derive clinical benefit, at the discretion of the investigator.
- In case a trial participant becomes pregnant during the study the IMP should be discontinued. The pregnancy will be followed as described in Section 5.2.6.2.3
- If peripheral neuropathy is suspected, treatment with spesolimab must be temporarily discontinued until a full neurological investigation has been conducted. After completion of the neurological investigation, treatment can be restarted based on medical judgement of the investigator

In case the infusion of study drug is permanently discontinued before the whole amount of the prepared solution has been administered to the trial participant, every effort should be made to complete all remaining study assessments of the visit.

Trial participants who discontinue treatment permanently and prematurely prior to the planned EoT visit should be registered as discontinued from treatment in IRT. These participants should follow the scheduled visits as much as possible as defined in the Flowchart: the EoT visit procedures should be conducted either immediately or as soon as

c40061625-02

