Infections (serious, severe, opportunistic)

Inhibition of the immune response with an immunemodulating biologic may increase the risk of this trial. Patients with any relevant chronic or acute infections.

A recent characterisation of individuals with homozygous IL-36R KO mutations revealed that normal immune function was broadly preserved suggesting that IL-36 signaling pathway inhibition may not substantially compromise host defenses [R17-3632].

In clinical trials with spesolimab, a higher proportion of patients with mild to moderate infections was seen in the spesolimab treatment group than in the placebo treatment group.

Nevertheless, there was no indication of an increased frequency of patients with severe, serious, and opportunistic infections in association with spesolimab treatment.

Screening procedures for infections are defined for this trial. Patients with any relevant chronic or acute infections including human immunodeficiency virus (HIV), viral hepatitis or tuberculosis are excluded from the trial. Treatment of infections should be initiated promptly according to standards of care.

Severe infections and opportunistic infections are considered AESIs for this trial; see Section 5.2.6.1.4. These conditions and serious infections are subject to close monitoring.

Page 34 of 177

Proprietary confidential information © 2023 Boehringer Ingelheim International GmbH or one or more of its affiliated companies

Table 1.4.2: 1 Overview of trial-related and potential risks (cont.)

Malignancies	Inhibition of the immune response with an immunomodulatory drug may potentially impair immune defences and thus theoretically decrease immune defence against malignancies.
	A recent characterisation of individuals with

A recent characterisation of individuals with homozygous IL-36R KO mutations revealed that normal immune function was broadly preserved suggesting that IL-36 signaling pathway inhibition does not compromise host defenses [R17-3632]

Patients with a recent history of malignancy will be excluded from participation in this trial. In case of occurrence of malignant neoplasm other than appropriately treated basal cell carcinoma or squamous cell carcinoma of the skin or in situ carcinoma of uterine cervix, the investigator should discontinue treatment with spesolimab. Diagnostics and treatment have to be initiated according to local standard of care.

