# 4.2 OTHER TREATMENTS, EMERGENCY PROCEDURES, RESTRICTIONS

#### 4.2.1 Other treatments and emergency procedures

Systemic hypersensitivity including and anaphylactic reaction
In case of systemic hypersensitivity including and anaphylactic reaction emerging during or after of trial medication, the investigator should consider in accordance with severity of the reaction and local standard of care to

- Immediately interrupt the
- Treat with systemic antihistamines, i.v. steroids, and in case of a severe allergic reaction (eg, anaphylactic reaction) epinephrine

Also draw a plasma sample for IgE and ADA as detailed in the Laboratory Manual (ISF). Please initiate the evaluation of histamine, serum tryptase, and complement components.

In case of	based on tri	al participant's clinical
course and medical judgment, the	be re-initiated/the	be
continued in case of mild or moder	ate	(according
to Common Terminology Criteria f	for Adverse Events (CTCAE) g	rading in section of the
ISF) at lower speed with gradual in	crease to complete the	as detailed in
the Instructions for Preparation and	Handling of spesolimab/place	bo in the ISF. In any case,
the total duration of should	d not exceed	Information about the
maximum time between the start of		
trial participant is de	etailed in the Instructions for Ph	narmacist filed on the ISF.

In case of anaphylactic reaction based on the criteria discussed in the statement paper from Sampson HA (Appendix 10.20 [R11-4890]) suspected to be caused by the trial medication, the investigator should permanently discontinue treatment with spesolimab. When a delayed hypersensitivity reaction is suspected, please draw a blood sample for laboratory assessment and evaluate for signs of extra-cutaneous organ involvement. The decision to discontinue treatment and/or restart treatment after resolution of the reaction should be based on reaction type and severity. See Section 3.3.4 for reference.

Severe infections (according to CTCAE grading in Section 15 of the ISF), serious infections, opportunistic or mycobacterium tuberculosis infections

Treatment of the infection should be initiated promptly according to local standard of care. No further trial medication should be administered until the active infection has been resolved. Treatment with spesolimab may be restarted when the trial participant has recovered according to investigator's assessment. See Section 3.3.4 for reference.

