# 5.2.6.1.2 Serious adverse event

A SAE is defined as any AE, which fulfils at least one of the following criteria:

- Results in death.
- Is life-threatening, which refers to an event in which the participant was at risk of death at the time of the event; it does not refer to an event that hypothetically might have caused death if more severe.
- Requires inpatient hospitalisation or prolongation of existing hospitalisation.
- Results in persistent or significant disability or incapacity.
- Is a congenital anomaly/birth defect.
- Is deemed serious for any other reason if it is an important medical event when based on appropriate medical judgement which may jeopardise the participant and may require medical or surgical intervention to prevent one of the other outcomes listed in the above definitions. Examples of such events are intensive treatment in an emergency room or at home for allergic bronchospasm, blood dyscrasias or convulsions that do not result in hospitalisation or development of dependency or abuse.

For Japan only: an event that possibly leads to disability will be handled as "deemed serious for any other reason" and, therefore, reported as an SAE.

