# The following are considered as AESIs:

Systemic hypersensitivity including infusion reaction and anaphylactic reaction
Any suspicion of severe infusion reaction systemic/hypersensitivity reaction and of any
potential cases of anaphylaxis should be defined and assessed using the criteria discussed in
the statement paper from Sampson HA (Appendix 10.20 [R11-4890]), see Section 4.2.1 for
"Other treatments and emergency procedures".

Severe infections (according to CTCAE grading in Section 15 of the ISF) (See Section 4.2.1 for "Other treatments and emergency procedures")

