#### 10.21 **COVID-19 RISK ASSESSMENT**

Table 10.21: 1 Overview of trial-related risks due to COVID-19

Possible or known risks of clinical relevance for this trial	Summary of data, rationale for the risk	Mitigation strategy
Investi	gational Medicinal Product: BI	655130
SARS-CoV-2 infection	Similar to other immune modulating biological treatments, spesolimab may potentially increase the risk of infections. However, the available pharmacological, non-clinical and clinical data do not indicate an increased risk of contracting SARS-CoV-2 or severe clinical courses due to the treatment with BI 655130. Furthermore, according to the Centers for Disease Control and Prevention there is limited information regarding risk factors for severe COVID-19 disease. However, based on currently available information and clinical expertise, older adults and people of any age who have serious not well controlled underlying medical conditions might be at higher risk for severe illness from COVID-19. So, participants with moderate to severe Hidradenitis suppurativa may be at risk of a severe clinical course of COVID-19.	Even though the risks associated with BI 655130 treatment are considered low, risk mitigation measures, such as exclusion of patients with increased risk of infections, close monitoring of AEs, as well as guidance on handling of acute infections occurring during the trial have been included in the spesolimab clinical trial protocol (CTP), please refer to Section 1.4.2.1. Also, potential participants with active or recent SARS-CoV-2 infection will only be included upon full recovery (see Section 3.3.3). A suspected SARS-CoV-2 infection while in the trial will be confirmed with an immediate PCR or antigen test. If positive, the participant will follow the local quarantine rules and should be treated, as any other acute infection, with standard of care. Trial treatment may be continued based on the discretion of the investigator (see Section 3.3.4.1). Then, treatment may be resumed following recovery from SARS-CoV-2 infection if clinical benefit is expected.

1061625-02 Clinical Trial Protocol Page 165 of 177
Proprietary confidential information © 2023 Boehringer Ingelheim International GmbH or one or more of its affiliated companies

Table 10.21: 1 Overview of trial-related risks due to COVID-19 (cont.)

Possible or known risks of clinical relevance for this trial	Summary of data, rationale for the risk	Mitigation strategy			
	Trial procedures				

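### For severe or serious SARS-CoV-2 infection, Section 4.2.1 withholds dosing until resolution, while Section 3.3.4.1 and Appendix 10.21 leave continued dosing to the investigator

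*Protocol*

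**What the plan says.** Three places in the protocol govern dosing during an infection.

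- **Section 4.2.1 (other treatments and emergency procedures).** The paragraph is headed "Severe infections (according to CTCAE grading in Section 15 of the ISF), serious infections, opportunistic or mycobacterium tuberculosis infections". Its rule is "No further trial medication should be administered until the active infection has been resolved". The investigator's assessment enters only at restart, once the participant has recovered. SARS-CoV-2 is not exempted. The paragraph closes by referring the reader to Section 3.3.4.
- **Section 3.3.4.1 (discontinuation of trial treatment).** One bullet covers any SARS-CoV-2 infection confirmed by local standards, of whatever grade, or "any significant systemic infection based on the investigator's judgement, interruption of study medication should be considered". Resumption after recovery is at the investigator's discretion. The bullet does not mention Section 4.2.1.
- **Appendix 10.21 (COVID-19 risk assessment), Table 10.21: 1.** After a positive test, quarantine and standard of care, the text is "Trial treatment may be continued based on the discretion of the investigator (see Section 3.3.4.1"). The next sentence allows treatment to be resumed after recovery where benefit is expected.

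**The concern.** Section 4.2.1 withholds the drug. The other two texts leave dosing to judgement and contain no carve-out for severe or serious cases. The severe case is foreseen, because the same table says "So, participants with moderate to severe Hidradenitis suppurativa may be at risk of a severe clinical course of COVID-19". A site that looks up the COVID-specific text is sent to Section 3.3.4.1, the weaker rule, and may give an immunomodulator during an infection that Section 4.2.1 says should first resolve.

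A dose given then cannot quickly be undone. Section 1.2 reports a terminal half-life of 28.8 days in healthy volunteers and a residual effect period of 16 weeks. Sites may also handle the same event differently, and a monitor could not say which conduct is the deviation.

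**Working it through.** No arithmetic decides this point. The check is to apply the texts to one participant and see whether any wording ranks them.

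**Test case.** A participant is hospitalised with confirmed SARS-CoV-2 infection when a dose is due. Section 5.2.6.1.2 lists among the criteria for a serious event "Requires inpatient hospitalisation or prolongation of existing hospitalisation", so this is a serious infection.

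| Text | Does it apply? | What it says about the dose |
|---|---|---|
| Section 4.2.1 | Yes: serious infection, no SARS-CoV-2 exemption | Withhold until resolved |
| Section 3.3.4.1 | Yes: confirmed SARS-CoV-2, any grade | Consider interrupting |
| Appendix 10.21 | Yes: positive test during the trial | May continue at discretion |

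**Do the cross-references rank them?**

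1. On continued dosing, Appendix 10.21 cites only Section 3.3.4.1.
2. On handling acute infections, Appendix 10.21 cites Section 1.4.2.1. That section holds no handling rule and refers back to Appendix 10.21, so the reference is circular.
3. Section 4.2.1 refers to Section 3.3.4, which contains the discretionary bullet.
4. In the Section 3.3.4.1 list, the suicidality bullet names Section 4.2.1 as the place for event-specific stopping rules. The infection bullet has no such pointer.
5. In that list, suspected peripheral neuropathy carries a mandatory temporary stop. The list states a firm hold where one is meant, so the infection bullet reads as real discretion.

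**Does other wording in Appendix 10.21 limit the permission?** The comparison with any other acute infection concerns how the infection is treated, not study drug. The sentence on resuming after recovery covers those who were interrupted. Neither narrows the permission to continue.

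**Where there is no conflict.** For SARS-CoV-2 infection that is neither severe nor serious, Section 4.2.1 does not apply and only the discretionary rule operates.

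**Reach.** Section 6.2.2 places administration from Visit 2 to Visit 31, so at most 31 − 2 + 1 = 30 dosing visits. The exact dosing visits are redacted in the flowchart, so this is an upper bound on opportunities and says nothing about frequency.

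**The case against.** The strongest reply is that all three texts can be followed at once. Two of them only permit; none tells anyone to dose. An investigator who withholds in a severe case complies with all of them. That is correct: this is an instruction against a permission, not two incompatible duties. But an investigator who doses can also point to a text that expressly allows it, and that is the conduct Section 4.2.1 is meant to prevent.

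A second reply is that the rules form tiers: discretion in general, and the hold once an infection is severe or serious. The list of adverse events of special interest supports this, since its entry reads "Severe infections (according to CTCAE grading in Section 15 of the ISF) (See Section 4.2.1" and so sends the reader to the hold. For other infections this reading is reasonable, and the point is weaker there. For SARS-CoV-2 it is not secure. Section 4.2.1 is the more specific text by severity and Appendix 10.21 the more specific by pathogen, and nothing chooses between them.

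Third, practical exposure is narrow. Doses are given at scheduled site visits, with home nursing optional for nine of them. Participants who test positive follow local quarantine rules. Severe infections and serious events must reach the sponsor within 24 hours, and many investigators would withhold anyway. This stands and limits the size of the problem.

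Fourth, no harm is shown. Table 1.4.2: 1 reports more mild to moderate infections on spesolimab, but also that "there was no indication of an increased frequency of patients with severe, serious, and opportunistic infections in association with spesolimab treatment". Appendix 10.21 adds that available data do not indicate more severe COVID-19 courses due to the drug. This also stands.

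**Conclusion.** The concern holds. For severe or serious SARS-CoV-2 infection the protocol both withholds dosing until resolution and permits it at discretion, and no text settles which applies. To a lesser degree the same looseness touches other severe, serious, opportunistic or tuberculosis infections, because the Section 3.3.4.1 bullet does not point to Section 4.2.1.

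The effect is on participant safety and consistent site conduct. Sample size, type I error and the planned efficacy analyses are untouched. The number of participants affected cannot be derived from the documents. The conclusion assumes that no site manual or investigator file, which are not available here, already ranks the rules. It should be fixed because the case is foreseen and the correction is simple, not because harm has been observed.

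**What to change.** Make the existing Section 4.2.1 hold govern; no new rule is needed.

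1. Add to the infection bullet in Section 3.3.4.1: *For an infection that is severe (CTCAE), serious, opportunistic or due to mycobacterium tuberculosis, SARS-CoV-2 included, trial medication is withheld until it has resolved (Section 4.2.1). Interruption on the investigator's judgement applies to other infections only.*
2. Replace the sentence on continued treatment in Appendix 10.21 with: *Dosing may go on at the investigator's discretion only where the infection is neither severe (CTCAE) nor serious; otherwise it is withheld until resolution (Sections 3.3.4.1 and 4.2.1).*

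**Cost.** Two short text changes and a letter to sites, with no new assessments. Section 6 already foresees an amendment for Part 2, which could carry the changes. That amendment is not assured, since Section 2.1.1 makes Part 2 conditional on the Part 1 results. Participants still being dosed in Part 1 may therefore need a small amendment of their own, with the approvals required by Section 8.1 across approximately 40 countries. The administrative effort is then larger, but the change itself stays small.

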#### **Clinical Trial Protocol**

Page 57 of 177

Proprietary confidential information © 2023 Boehringer Ingelheim International GmbH or one or more of its affiliated companies

possible, followed by the Follow-up visit (EoS) after the last trial drug administration date. All efforts should be made to keep the trial participant in observation for at least after the last dose of the study drug for safety reasons. All trial participants should have an EoS visit and assessments as per Flowchart must be done during the EoS visit.

For all trial participants, the reason for permanent discontinuation from trial treatment (e.g. AEs) must be recorded according the options available in the CRF. This data will be included in the trial database and reported.

In the event of force majeure or other disrupting circumstances (e.g. pandemic, war; please see Section 6), physical participant visits to the sites may not be feasible or may need to be restricted to ensure participant safety. Based on a thorough assessment of the benefits and risks, the investigator may still decide to continue trial treatment. Where permitted by local law and regulations, trial medication may be shipped directly to the participants' home in agreement with the sponsor. In that case, a home visit service would assist the participant with medication administration. In case these options cannot be locally implemented, the IMP will be temporarily discontinued.

When new efficacy or safety information becomes available, Boehringer Ingelheim will review the benefit-risk-assessment and, if needed, pause or discontinue the trial treatment for all trial participants or take any other appropriate action to guarantee the safety of the trial participants.

